 - Any factors that increase the risk of QTc prolongation or risk of arrhythmic events such as heart failure, hypokalaemia, congenital long QT syndrome, family history of long QT syndrome or unexplained sudden death under 40 years-of-age, or any concomitant medication with known or possible risk of QT interval prolongation
 - Patients with an ejection fraction (EF) $<55\%$ or the lower limit of normal of the institutional standard will be excluded. Only in cases where the Investigator (or the treating physician or both) suspects cardiac disease with negative effect on the EF, will the EF be measured during screening using an appropriate method according to local standards to confirm eligibility (e.g., echocardiogram [ECHO], multi-gated acquisition scan [MUGA]). A historic measurement of EF no older than 6 months prior to first administration of study drug can be accepted provided that there is clinical evidence that the EF value has not worsened since this measurement in the opinion of the Investigator or of the treating physician or both.
11. Out of range laboratory values are defined as:
 - Alanine transaminase (ALT) and aspartate amino transferase (AST) >3 times the ULN if no demonstrable liver metastases or >5 times ULN in the presence of liver metastases
 - Total bilirubin >1.5 times ULN, except for patients with Gilbert's syndrome who are excluded if total bilirubin >3.0 times ULN or direct bilirubin >1.5 times ULN
12. Human immunodeficiency virus (HIV) infection, acute or chronic viral hepatitis
13. Known hypersensitivity to the trial drugs or their excipients
14. Serious concomitant disease or medical condition affecting compliance with trial requirements or which are considered relevant for the evaluation of the efficacy or safety of the trial drug, such as cardiac, neurologic, psychiatric, infectious disease or active ulcers (gastro-intestinal tract, skin) or laboratory abnormality that may increase the risk associated with trial participation or trial drug administration, and in the judgment of the Investigator and/or Medical Monitor would make the patient inappropriate for entry into the trial.
15. Chronic alcohol or drug abuse or any condition that, in the Investigator's and/or Medical Monitor's opinion, makes them an unreliable trial patient or unlikely to complete the trial
16. Women who are pregnant, nursing, or who plan to become pregnant while in the trial and for at least 6 months after the last administration of trial medication.

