Rationale for change		Update BI 891065 tablet strengths in this study because 100 mg tablet will become available. It will not be distributed to countries until all local regulatory requirements for adding a new dose strength are met.
Section to be changed		Figure 4.1.7: 1 Schematic of dose delays and reductions
Description of change		Modified box BI 891065: Restart at original dose or at one dose level lower* Figure footnote: If deemed Investigator to decide based on what is in the best interest of the patient, may restart at original assigned dose.
Rationale for change		To clarify criteria for restarting at original or a lower dose after a dose interruption
Section to be changed		Figure 4.1.7 Dose reduction and dose delays
Description of change		A maximum of 2 dose reductions of BI 891065 are allowed, if lower tested dose levels are available. Dose reductions will be only to doses previously explored in earlier cohorts if the Investigator anticipates a lower dose would be better tolerated.
Rationale for change		To clarify criteria for dose reduction of BI 891065
Section to be changed		Section 5.2.3 Safety laboratory parameters
Description of change		The standard haematology panel will consist of:

		haemoglobin, red blood cell count, haematocrit, mean corpuscular volume, white blood cell count, and differential blood count (preferably expressed in absolute values), and platelets, haptoglobin and reticulocytes.
Rationale for change		To investigate the reason for isolated bilirubin increases observed.
Section to be changed		Section 5.2.4 Electrocardiogram
Description of change		In Part C, single ECGs will typically be taken unless additional triplicate readings are required with pharmacokinetic sample collection as indicated in Table 10.3: 3. When triplicate ECGs are not done, single readings will be done for safety purposes as indicated in Part C Lung Flow Chart.
Rationale for change		To clarify timing of single and triplicate ECG collections in Part C.
Section to be changed		Section 5.2.6.4.3 Cytokine release syndrome

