URATE	Uric Acid	High	Females: >600 umol/L and >baseline Males: >650 umol/L and >baseline CTCAE based upon AE

¹A= CTCAE grade 2 or greater with an increase of at least one CTCAE grade from baseline

²CTCAE grading will not consider symptoms presence of bleeding or use of anticoagulation.

Handling of CTCAE grade -1 and -9 laboratory parameters:

Generally, in case only one direction of worsening (high or low laboratory value) is specified in the CTCAE document, there is no need to examine the other direction. Therefore, for

calculating the change in CTCAE grade, patients with a CTCAE grade of -9 (no CTCAE grade defined) will be automatically treated as CTCAE grade 0 for all analyses. In laboratory listings, the CTCAE grade will be displayed as -9.

There are certain parameters for which CTCAE grades can only be differentiated by taking physiological consequences into account. These laboratory values will be coded as -1. As these definitions aggregate laboratory data and adverse events or concomitant therapies no analyses based on CTCAE grades will be done. Instead standard laboratory analyses as for laboratory parameters without CTCAE grade definitions will be done. Nevertheless, a laboratory listing including -1 values will be added to the CTR.

Corrected calcium:

The grading of hypocalcemia is based on corrected calcium as calcium can be falsely low if hypoalbuminemia is present. The following corrective calculation will be performed:

$$\text{Corrected calcium (mg/dL)} = \text{Total Calcium (mg/dL)} - 0.8[\text{Albumin (g/dL)} - 4]$$

No correction of the reference range has to be done. The reported reference range of total calcium will be used for analyses. Corrected calcium can be only derived at a certain time point in case both laboratory values total calcium and albumin have been reported for the patient in the same laboratory sample.

Hepatic enzyme elevations (potential Hy's law cases):

These are defined as those cases where a combination of all of the following events occurred: any on-treatment value of ALT and/or AST > 3ULN (upper limit of normal) with total bilirubin \geq 2ULN and ALP < 2ULN. The events can occur in any order, but must occur within 14 days of the previous event, i.e. the second event must occur within 14 days of the first event, and the third event must occur within 14 days of the second event, etc. Patients with missing laboratory values for liver enzymes will be excluded from these analyses, but presented separately.

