Tabulations of hepatic enzyme elevations and liver laboratory values will be done according to the FDA Drug Induced Liver Injury (DILI) guidance ([10](#)).

Hepatic enzyme elevations will be displayed for the treated set for the whole on-treatment period.

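### The SAP's screen for potential Hy's law cases has no baseline reference, although entry criteria admit patients who already meet one of its limits, so it cannot separate new changes from entry status

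*SAP*

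**What the plan says.** SAP 7.8.2, under hepatic enzyme elevations, defines a potential Hy's law case by three on-treatment limits: "any on-treatment value of ALT and/or AST > 3ULN (upper limit of normal) with total bilirubin" at or above "2ULN and ALP < 2ULN". On timing it adds: "The events can occur in any order, but must occur within 14 days of the previous event". On population and period: "Hepatic enzyme elevations will be displayed for the treated set for the whole on-treatment period". The definition contains no baseline value and no change from baseline.

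Protocol 3.3.3, exclusion criterion 11, sets the entry limits. ALT and AST exclude a patient when ">3 times the ULN if no demonstrable liver metastases or >5 times ULN in the presence of liver metastases". Total bilirubin excludes above 1.5×ULN, with an exception for patients with Gilbert's "syndrome who are excluded if total bilirubin >3.0 times ULN or direct bilirubin >1.5 times ULN". Neither criterion 11 nor the other laboratory criterion (21) limits ALP.

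Elsewhere in SAP 7.8.2 baseline is used. The primary laboratory tests get changes from baseline, and ALP, ALT, AST and bilirubin get shift tables in multiples of the upper limit. In SAP Table 7.8.2: 1, creatinine, LDH, urea nitrogen, TSH and others count as potentially significant only if the value is also worse than baseline. ALT, AST and bilirubin carry no such condition, and a footnote says CTCAE grades are not defined at baseline for them.

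**The concern.** A Hy's law screen is read as pointing to patients in whom hepatocellular enzymes and bilirubin have both risen. Here one of those two elements can be an entry characteristic. A patient with liver metastases and stable ALT of 4×ULN looks the same in the table as a patient whose ALT went from normal to 4×ULN.

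This trial gives a specific reason to care. Protocol Section 11 (global amendment 5, entry for Section 5.2.3) records that haptoglobin and reticulocytes were added to the haematology panel for this reason: "To investigate the reason for isolated bilirubin increases observed". An isolated bilirubin rise is exactly what would turn a standing, metastasis-related enzyme elevation into a potential case. The extra tests help to explain such a rise, but the Hy's law table as specified does not show which cases arose that way.

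At stake is how well a reader can interpret a small hepatic safety table.

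**Working it through.** The plan states no figure for this rule, so there is nothing to reproduce. The check compares the entry limits with the case limits.

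**Inputs (multiples of ULN)**
- Case rule, SAP 7.8.2: ALT/AST > 3, total bilirubin ≥ 2, ALP < 2.
- Entry, criterion 11: ALT/AST ≤ 3, or ≤ 5 with liver metastases; total bilirubin ≤ 1.5, or ≤ 3 in Gilbert's with direct bilirubin ≤ 1.5.

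**Overlap by entry group (ALP < 2 required throughout)**

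| Entry group | ALT/AST limit already met? | Bilirubin limit already met? | Smallest change that makes a potential case |
|---|---|---|---|
| Neither condition | No (≤ 3) | No (≤ 1.5) | Both must rise |
| Liver metastases only | Possible (> 3 to 5) | No (≤ 1.5) | Bilirubin alone, to ≥ 2 |
| Gilbert's only | No (≤ 3) | Possible (2 to 3) | ALT/AST alone, to > 3 |
| Both | Possible (> 3 to 5) | Possible (2 to 3) | None |

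**Worked patients (ALT / total bilirubin, ALP 1.0)**
- Metastases, 4.0 / 1.0 moving to 4.0 / 2.0: potential case, enzyme unchanged. From an entry bilirubin of 1.5, the rise needed is 2.0 − 1.5 = 0.5.
- Metastases and Gilbert's, 4.0 / 2.5 throughout: potential case with no change.
- Neither condition, 1.0 / 1.0 moving to 4.0 / 2.0: potential case, both risen.

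All three enter the count identically.

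**How rare is the no-change route?** The documents give no prevalences, so these are assumptions, taken as independent: Gilbert's 3–10%; liver metastases 30–60%; ALT/AST > 3×ULN among those with metastases 5–20%; bilirubin ≥ 2×ULN among those with Gilbert's 20–50%. The number of patients is the planned 30 (Part A) plus the upper planned 37 (Part B) = 67. The SAP states that Part C enrolled no one.
- Low: 0.03 × 0.30 × 0.05 × 0.20 = 0.00009; × 67 = 0.006 patients.
- High: 0.10 × 0.60 × 0.20 × 0.50 = 0.006; × 67 = 0.40 patients.

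ALP < 2×ULN is taken as always met, so the true figure could only be lower. No comparable estimate is offered for the single-condition routes: the documents give neither the number with raised baseline enzymes nor the size or number of the isolated bilirubin increases.

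**The case against.** The strongest reply is that this is only a screen. The SAP calls these potential cases, and attribution is handled elsewhere. Protocol 5.2.6.4.5 sends such patients to a DILI checklist, and its Hy's law description requires that no other cause, including pre-existing liver disease, explains the values. The protocol's hepatic injury definition (5.2.6.4.5) and its hepatic DLT criterion (4.1.8) also use multiples of ULN without baseline, so the SAP is consistent with them. A screen should favour sensitivity. Changes from baseline, shift tables and separate direct and indirect bilirubin are already planned.

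Much of this stands, and it rules out several stronger readings that a reader might infer:
- That such patients are reported as having drug-induced injury. The SAP's label does not say so.
- That the table could mislead dose selection. Dose decisions rest on DLTs reviewed case by case, with an exemption for events unequivocally due to the malignancy or an extraneous cause (Protocol 4.1.8), and on the Safety Review Committee's look at patient profiles (3.1).
- That the distortion is 12.5% to 33% of a cohort. Those are just 1/8 and 1/3, the share that one case takes in a cohort of 8 or 3. They say nothing about how likely a case is.
- That the count should be limited to patients above their own baseline. If both values had to exceed baseline, a patient with stable ALT of 4×ULN and bilirubin going from 1 to 5×ULN would vanish from a safety screen. If any excess sufficed, 4.0 to 4.1×ULN would pass and little specificity would be gained.

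What the reply does not meet is the missing joint view. The shift tables are described analyte by analyte, and the SAP describes no display that connects the combined count to baseline. The cited DILI guidance, the sponsor's laboratory standard and the table shells may do so, but they are not among the documents.

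**Conclusion.** The point holds as a limit on specificity. The rule ignores baseline, and eligibility lets one of its two hepatic limits be met before the first dose: the enzyme limit with liver metastases, the bilirubin limit in Gilbert's syndrome. In either group a change in one value alone is enough, provided ALP is below 2×ULN. For patients with neither condition the rule works as intended, because both values must rise.

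Meeting the whole rule with no change is possible but rare: 0.006 to 0.4 patients expected among 67, on assumed and independent prevalences. The single-condition routes are the practical matter, and their frequency cannot be derived from the documents. The effect is confined to a descriptive screening table; the MTD, the DLT counts and the response analyses are untouched. This is a modest and inexpensive improvement to the SAP.

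**What to change.** In SAP 7.8.2:
1. Keep the unadjusted count of potential Hy's law cases in the treated set as the main screen.
2. Also present it split by baseline status: ALT and AST ≤ 3×ULN with total bilirubin < 2×ULN, versus all others.
3. For each potential case, list baseline and on-treatment ALT, AST, total and direct bilirubin and ALP.
4. State that no case is removed from the count because of its baseline.

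No new data are needed: Protocol 5.2.3 already collects these tests, and SAP 6.7 already defines the laboratory baseline. The cost is one extra table split and one listing. The subgroups will be small, so the split should be read with the listing and not as a comparison of rates.

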4.1.8 Definition of dose-limiting toxicity

Dose-limiting toxicities (DLTs) will be recorded throughout the trial. Any DLT must be reported to the [REDACTED] Medical Monitor by the Investigator or designee within 24 hours of first knowledge, and to the [REDACTED] as an SAE when appropriate. All DLTs will be agreed upon between the Sponsor, the Study Chair, the [REDACTED] Medical Monitor, and the Investigators after review of the data from each cohort. Only DLTs starting in the first cycle of monotherapy during Part A or during the first cycle of BI 891065 in combination with BI 754091 during Part B are necessary for dose-escalation decisions made by the SRC. DLT information from later cycles will be taken into consideration if available.

All relevant safety information (including DLTs) together with data on target engagement will be considered when selecting the recommended doses for the expansion cohorts.

Severity of AEs will be graded according to CTCAE Version 5.0. Any of the following AEs will be classified as DLTs following review by the Investigators and the [REDACTED] Medical Monitor unless unequivocally due to underlying malignancy or an extraneous cause.

Haematologic toxicities:

- For patients with solid tumours:
 - Any Grade 5 toxicity
 - Neutropenia \geq Grade 4 lasting for >5 days
 - Febrile neutropenia of any duration (ANC $<1.0 \times 10^9$ cells/L and fever $\geq 38.5^\circ\text{C}$)
 - Neutropenia Grade 3 with documented infection
 - Grade 4 thrombocytopenia, or Grade 3 thrombocytopenia with bleeding or a requirement for platelet transfusions
 - Grade 4 anaemia unexplained by underlying disease.

Non-haematological toxicities:

- AST or ALT >3 times ULN and concurrent total bilirubin >2 times ULN without initial findings of cholestasis (e.g., findings consistent with Hy's law or the FDA definition of potential DILI)
- \geq Grade 4 AST or ALT of any duration
- Any \geq Grade 3 non-haematologic toxicity with the following exceptions:
 - Grade 3 irAE that resolves to \leq Grade 1 or to baseline with immunosuppressive therapy within 2 weeks
 - Grade 3 fatigue that persists <7 days
 - Grade 3 rash that resolves to \leq Grade 1 within 2 weeks
 - Grade 3 or 4 elevation in serum amylase and/or lipase that is not associated with clinical or radiographic evidence of pancreatitis
 - Grade 3 electrolyte abnormality that lasts <72 hours, is not clinically complicated, and resolves spontaneously or responds to conventional medical intervention

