5.2.6.4.5 Hepatic injury

A hepatic injury is defined by the following alterations of hepatic laboratory parameters:

- an elevation of AST and/or ALT ≥ 3 fold ULN combined with an elevation of total bilirubin ≥ 2 fold ULN measured in the same blood draw sample, and/or
- aminotransferase (ALT, and/or AST) elevations ≥ 10 fold ULN

These lab findings constitute a hepatic injury alert and the patients showing these lab abnormalities need to be followed up according to the “Potential DILI checklist” provided in the ISF.

In case of clinical symptoms of hepatic injury (icterus, unexplained encephalopathy, unexplained coagulopathy, right upper quadrant abdominal pain, etc.) without lab results (ALT, AST, total bilirubin) available, the Investigator should make sure these parameters are analysed, if necessary in an unscheduled blood test. Should the results meet the criteria of hepatic injury alert, the procedures described in the Potential DILI checklist should be followed.

Lab values meeting this definition of hepatic injury will need to be reported as an AESI. Please follow the flowchart below (Figure 5.2.6.4.5: 1) for reporting hepatic injury / potential DILI cases.

[figure not shown]

Figure 5.2.6.4.5: 1 Processing Potential DILI cases in oncology

Hy's Law cases have the following 3 components:

- The drug causes hepatocellular injury, generally shown by a higher incidence of 3-fold or greater elevations above the ULN of ALT or AST
- Among trial subjects showing such aminotransferase elevations, often with elevations much greater than 3 times ULN, one or more also show elevation of serum total bilirubin to >2 times ULN, without initial findings of cholestasis (elevated serum ALP)

- No other reason can be found to explain the combination of increased aminotransferase and total bilirubin, such as viral hepatitis A, B, or C; pre-existing or acute liver disease; or another drug capable of causing the observed injury.

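### SAP 7.8.2 can count a patient with ALP ≥2×ULN at the liver elevation as a potential Hy's law case, because an ALP <2×ULN from another day within 14 days satisfies the rule

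*SAP*

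**What the plan says.** The rule is in SAP 7.8.2, in the paragraph on hepatic enzyme elevations. It opens: "These are defined as those cases where a combination of all of the following events occurred". The criteria are "any on-treatment value of ALT and/or AST > 3ULN (upper limit of normal) with total bilirubin" at or above "2ULN and ALP < 2ULN". On timing it says "The events can occur in any order, but must occur within 14 days of the previous event", and goes on to require that "the third event must occur within 14 days of the second event, etc". Only three criteria are listed, so the third event can only be one of those three, and ALP <2×ULN is one of the chained events. No sentence ties ALP to the sample that carries the ALT/AST or bilirubin elevation, and none disqualifies a case because ALP is ≥2×ULN there.

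The remaining text sends patients with missing liver enzymes to a separate presentation, points to the FDA DILI guidance for the tabulations, and applies the display to the treated set over the whole on-treatment period. It sets no timing for ALP.

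The protocol describes the pattern differently. The DLT criterion in 4.1.8 pairs ALT/AST >3×ULN with "concurrent total bilirubin >2 times ULN without initial findings of cholestasis". The Hy's law description in 5.2.6.4.5 also requires that there be no initial cholestasis, and names raised ALP as its sign.

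**The concern.** ALT/AST and bilirubin elevations happen at a point in time. ALP <2×ULN does not: it states that cholestasis is absent, and it is informative only when it describes the injury being classified. If any nearby ALP value can meet it, a patient whose ALP rises together with ALT/AST and bilirubin is put in the same count as a patient with a hepatocellular pattern.

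Such patients are foreseeable here. Part B admits pancreatic cancer (Protocol 3.3.2), ALT/AST up to 5×ULN is allowed at entry with liver metastases, and the laboratory exclusions set no ALP limit (Protocol 3.3.3). In a first-in-human trial, the potential Hy's law count is a line that readers go to first. Part C was cancelled without enrolling (SAP Section 4), so the point concerns Parts A and B.

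**Working it through.** No sample-size or power figure is involved. The check applies the rule literally to the sampling schedule.

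**Rule.** Take one date each for ALT/AST >3×ULN, bilirubin ≥2×ULN and ALP <2×ULN, and sort them as s1 ≤ s2 ≤ s3. The patient is a case if s2 − s1 ≤ 14 and s3 − s2 ≤ 14.

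**Scheduled biochemistry** (Protocol flow charts, 21-day cycles). Part A: Days 1, 8, 12, 15, then Day 1 of each cycle (Days 22, 43, 64, …). Part B: Days 1, 12, 15, then the same. The Day 1 sample is pre-dose and is baseline under SAP 6.7, so the first scheduled on-treatment sample is Day 8 in Part A and Day 12 in Part B.

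**Reach of the window, nominal days.**
- Part A, Days 8 to 22: widest separation 22 − 8 = 14 days. Any scheduled on-treatment ALP in this stretch is within reach of any elevation in it.
- Part B, Days 12 to 22: 22 − 12 = 10 days. The same holds.
- From Cycle 2 on: 43 − 22 = 21 days. With the ±2-day window used at both visits, 21 − 4 = 17 days, still more than 14. Two scheduled samples cannot be chained.

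**Hypothetical patients** (values are multiples of ULN). The last column reads ALP on the sample with the first qualifying elevation.

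| | Pattern | SAP rule | ALP at first elevation |
|---|---|---|---|
| A | Part A: Day 8 ALP 1.0; Day 15 ALT 6, bilirubin 3, ALP 4 | Counted (gap 7) | ≥2 row |
| B | Part B: Day 15 ALP 1.2; Day 22 ALT 6, bilirubin 3, ALP 4 | Counted (gap 7) | ≥2 row |
| C | Part A: Day 8 ALP 1.2; Day 15 ALT 4, ALP 4; Day 22 bilirubin 3, ALP 6 | Counted (gaps 7, 7) | ≥2 row |
| D | ALP ≥2 on every on-treatment sample; Day 8 ALT 5, bilirubin 3, ALP 3 | Not counted | ≥2 row |
| E | Day 43 ALP 1.0; Day 64 ALT 6, bilirubin 3, ALP 4 | Not counted (gap 21) | ≥2 row |
| F | Day 12 ALT 4, ALP 1.0; Day 15 ALT 6, bilirubin 3, ALP 1.2 | Counted | <2 row |
| G | Day 8 ALT 8, ALP 1.0; Day 15 bilirubin 3, ALP 2.1 | Counted | <2 row |

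Patients B and E have the same values on the sample showing the injury, and both had ALP <2×ULN at the preceding sample. One is counted and the other is not, only because the preceding sample was 7 days earlier in one and 21 in the other. The classification follows visit spacing, not the liver pattern.

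**The case against.** **Over-inclusion is the safe direction.** The SAP label says potential cases, the analysis is descriptive, ALP, ALT, AST and bilirubin also have shift tables by multiples of the upper reference limit (SAP 7.8.2), and patients meeting the hepatic-injury alert are followed individually (Protocol 5.2.6.4.5). All of this stands and keeps the consequence modest. It does not justify an ALP criterion that depends on sampling dates, and a two-row display gives up no sensitivity.

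**The protocol speaks of initial cholestasis, so an earlier ALP may be legitimate.** This stands in part. It is why ALP should not be read on the bilirubin sample: patient G had no initial cholestasis and would be dropped. But the any-order wording also accepts an ALP taken after the injury, so the SAP does not implement initial either.

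**The SAP defers to sponsor laboratory standards and the FDA DILI guidance.** Neither is available here, so whether they set an ALP time is unknown. The SAP nevertheless states its own explicit rule and does not say that another text overrides it.

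**Stronger readings that a reader might infer.**
- That the ALP criterion excludes almost nobody. Patients D and E show otherwise: persistently raised ALP is excluded, and from Cycle 2 scheduled samples are too far apart.
- That cases could routinely be assembled over 14 + 14 = 28 days. On nominal scheduled days the chain covers at most 14 days in Part A and 10 in Part B, so the full span needs unscheduled or end-of-treatment samples.
- That the table should agree with the AESI and DLT counts. The hepatic-injury AESI requires transaminase and bilirubin values "measured in the same blood draw sample" but has no ALP term, so it includes cholestatic cases by design. AESIs are analysed from eCRF reports (SAP 7.8.1), and DLTs are agreed case by case (Protocol 4.1.8). Different counts are expected.

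**Conclusion.** The point holds in a limited form. Followed literally, SAP 7.8.2 counts some patients whose ALP is ≥2×ULN at the ALT/AST and bilirubin elevation. It does so when a new ALP rise comes within 14 days of an on-treatment ALP <2×ULN, or when ALP falls below 2×ULN within 14 days afterwards. On scheduled visits this is confined to the first on-treatment sample through Cycle 2 Day 1. Later it needs unscheduled or end-of-treatment samples. The former are plausible in patients with abnormal liver values, since Protocol 10.2 recommends checks every 3 days for Grade 2 hepatitis.

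The number of patients affected cannot be derived from the documents. The error runs towards over-inclusion in one descriptive table. The MTD and DLT analyses (SAP 7.4) do not use this rule.

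The conclusion assumes that the rule is programmed as written, that the on-treatment restriction covers all three laboratory values, that the Day 1 sample is pre-dose, and that visits fall on nominal days except where the ±2-day window is applied.

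**What to change.** Reword the paragraph in SAP 7.8.2:
1. Apply the 14-day window only to the pair ALT/AST >3×ULN and total bilirubin ≥2×ULN, in either order.
2. Treat ALP as a condition, not an event. Read it on the sample with the first qualifying elevation of the pair, or on the nearest sample if ALP is missing there. This follows the protocol's reference to initial cholestasis. Patients with no usable ALP stay in the SAP's existing separate presentation.
3. Report pairs with ALP <2×ULN and pairs with ALP ≥2×ULN in two adjacent rows. State how a patient with more than one pair is classified.
4. Optionally flag pairs in which ALT/AST and bilirubin come from the same blood draw.

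The cost is a few lines of SAP text, one extra table row and some programming; no new data are needed. The headline row may hold fewer cases than under the present rule, but the others appear in the next row. Patients such as D and E, whom the present rule leaves out altogether, become visible there.
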